### **E. Monitor Log**

The **Site Monitoring Visit Log** (Appendix C) will be maintained throughout the course of the study. The log will contain the visit date, monitor name/signature and the purpose of the visit (i.e. site initiation, onsite interim monitoring (as applicable), site close-out, etc.). The site monitoring visit log will be filed in the site Regulatory Binder for the study.

## **F. Delegation of Authority (Site Signature Log)**

A **Delegation of Authority/Site Signature Log** (Appendix C) will be maintained throughout the study and will contain the names, initials, signatures and study responsibilities of all site personnel/designees involved in study procedures and data collection. This log will be filed in the site Regulatory Binder for the study.

## **G. Baseline/Pre-operative/Operative/Discharge Assessment**

Data collection required for baseline, operative, and discharge will be collected preoperatively if the subject signs their informed consent prior to surgery. If the subject meets all inclusion and none of the exclusion criteria and signs an informed consent prior to the end of the 6 weeks follow-up visit window, retrospective chart review will be conducted for preoperative data. At a minimum, this will include physical exam data, demographic data, and operative data. However, it may include additional information related to pain, function, and radiographic evaluation if available. The following case report forms will be collected baseline, operatively, and at discharge:

1. Enrollment Form
2. Demographic Evaluation
3. Operative Record
4. Postoperative Discharge Assessment
5. X-Rays (any available views)
6. Adverse Event(s)
7. Protocol Deviation(s)
8. Study Completion
9. Explanted Device

## **H. Post-Surgical Management**

Post-surgical management for study subjects will follow the investigator's standard of care for patients undergoing femoral neck or intertrochanteric fracture repair. Post-surgical rehabilitative therapy will be as prescribed by the investigator. The FDA cleared instructions for use and surgical technique must be followed for this product. Please refer to the latest versions of these documents on the zimmerbiomet.com website or contact your local clinical study manager or Zimmer Biomet sales associate for additional details.

## **I. Post-operative Follow-up Procedures (Data Collection)**

Post-operative clinical evaluations/assessments will be conducted at 1 to 6 weeks (+ 14 days), 3 months ( $\pm$  30 days), 6 months ( $\pm$  60 days), and 12 months ( $\pm$  90 days) post-surgery. The following case report forms will be collected at

each interval:

1. Postoperative Follow-up
2. VAS Pain
3. EQ-5D-5L
4. RUSH
5. FIX-IT
6. X-rays (A/P and lateral views of the hip or pelvis)
7. Physician Radiographic Assessment
8. Adverse Event(s)
9. Protocol Deviation(s)
10. Study Completion
11. Explanted Device

Subjects will be followed post-operatively for 12 months. Unless the study is otherwise closed, data will continue to be collected until the subject completes the study per the protocol, voluntarily withdraws from the study, is withdrawn from the study by the investigator, is lost to follow-up, undergoes revision to remove a study device, (due to complication) including partial removal i.e. screw, or expires. See Management of Incurrent Events for additional details. Reason(s) for study completion must be documented on the Study Completion case report form.

## **J. Minimization of Subjects Lost to Follow-up**

[figure not shown]
[figure not shown]
Subject follow-up is extremely important for the conduct of a clinical study, and the expectation is to maintain the highest possible rate of follow-up compliance throughout this study. During the informed consent process and at each follow-up interval, subjects should be counseled on the importance of completing future study follow-up intervals.

## **K. Radiographic Definitions and Methods**

All postoperative radiographic evaluations performed according to the protocol will be reviewed by the Investigator at the time of the evaluation and documented using the **Physician Radiographic Assessment** case report form. This includes documentation of any significant radiographic findings. In addition, an **Adverse Event** case report form must be completed for those findings indicated by an asterisk on the **Physician Radiographic Assessment** case report form, or for any other findings identified as an adverse event.

[figure not shown]
[figure not shown]
- Non-union definition: A total RUSH score below 18 at six month post-surgery is considered a non-union.

- RUSH scoring examples:

	Cortical Bridging	Cortical Fracture Line Disappearance
Anterior	1	2
Posterior	1	1
Medial	1	1
Lateral	1	1
Total:	4	5

Trabecular Consolidation	1
Trabecular Fracture Line Disappearance	1
RUSH Total:	11

	Cortical Bridging	Cortical Fracture Line Disappearance
Anterior	3	3
Posterior	2	2
Medial	2	2
Lateral	3	3
Total:	10	10

Trabecular Consolidation	3
Trabecular Fracture Line Disappearance	3
RUSH Total:	26

Acceptable views include A/P and lateral views of the hip and/or pelvis and must include view of the implanted devices and the treated fracture and/or healing or healed fracture.

At the Sponsor's discretion, study radiographs may be requested from the sites for independent radiographic review and assessment of appropriate parameters.

## **IX. Reporting**

The management of all study data received by the Sponsor will be the responsibility of the Sponsor or its Designee. The use or disclosure of all protected health information will comply with the Health Insurance Portability and Accountability Act (HIPAA). All information will be treated with strict adherence to professional standards of confidentiality and will be filed by the Sponsor under adequate security and restricted accessibility by clinical personnel. All electronic systems used to create, modify, maintain, or transmit study records will be validated according to 21 CFR Part 11(ii). Reports and communications relating to study subjects will typically identify each subject only by the subject's initials, assigned study subject Case ID number, date of surgery, operative side, and date of birth.

### **A. Prior to Initiation of the Study**

#### **1. Clinical Trial Agreement (CTA)**

A fully executed (signed by all required parties) CTA must be on file with the Sponsor prior to any investigator participating in this study.

#### **2. Institutional Review Board/Ethics Committee Protocol Approval**

This study protocol must be submitted to and approved by the Investigator's Institutional Review Board (IRB) or Ethics Committee (EC). A copy of the IRB or EC approval letter must be submitted to the Sponsor. The letter should identify the following:

- Protocol name and/or number
- Date of IRB or EC meeting (if available)
- Date of approval
- Date of expiration
- Signature of IRB or EC

**3. Informed Consent**

A Sponsor-approved Informed Consent template will be provided along with the study protocol for IRB or EC submission and approval. If the IRB or EC requires revisions to the provided Informed Consent, the requested revisions must be submitted by the Investigator to the Sponsor for review and approval. Once the Sponsor has reviewed and approved the revision, the Informed Consent will be re-submitted to the IRB or EC for final review and approval. A copy of the final IRB or EC approved Informed Consent form (ICF) must be submitted to the Sponsor.

**4. ClinicalTrials.gov Registration**

The Sponsor will be responsible for registering this study on [www.ClinicalTrials.gov](http://www.ClinicalTrials.gov) if required by local and national regulations.

**B. Clinical Data Collection/Submission**

**1. Summary of Case Report Form Data Collection**

- a. Study data will be collected on source documents which may include study-specific worksheets provided by the Sponsor. For subjects having bilateral proximal femur fracture treatment, separate case report forms must be completed for each operative side.
- b. The following source document/CRF completion guidelines should be followed:
  - i. Complete carefully and accurately.
  - ii. Complete header information consistently across all case report forms for each individual study subject (when study-specific CRFs are used).
  - iii. Be sure that data on the source documents match that which is entered through the electronic data capture (EDC) system
  - iv. Use the study subject's unique Case ID number assigned as instructed. Do not provide information that is not requested on the CRFs.
  - v. Ensure that all fields are completed. For fields completed by the subject, efforts should be made to obtain any missing responses prior to the subject completing their visit.

**2. Data Submission**

- a. Completed CRFs will be submitted directly to the Sponsor by electronic data capture and submission via a method approved by

the Sponsor. Every effort must be made to ensure data submission to the Sponsor is made within 30 days of the visit completion.

**3. Quality Assurance of Data**

- a. The Investigator should ensure the accuracy, completeness, legibility, and timeliness of the data reported to the Sponsor in the CRFs and in all required reports. Data reported on the CRF, which are derived from source documents, should be consistent with the source documents or the discrepancies should be explained. All electronic systems used to create, modify, maintain, or transmit electronic study records will be validated according to 21 CFR Part 11(ii). The Sponsor will maintain quality control systems, in accordance with the Sponsor's policies and procedures.

**C. Reporting Requirements**

**1. Investigator Reporting Responsibilities**

The Investigator should ensure the accuracy, completeness, legibility, and timeliness of data reported to the Sponsor in accordance with this protocol. The Investigator or Designee will provide periodic reports to their IRB or EC as required to maintain IRB or EC approval throughout the study, and will provide any required final reporting to the IRB or EC upon study completion/termination. A copy of all IRB or EC re-approval letters must be submitted to the Sponsor. If the IRB or EC terminates or suspends its approval of the study, the Investigator or Designee will suspend study-related activities and will promptly notify the Sponsor. The Investigator should also promptly provide written reports to the Sponsor and the IRB or EC regarding any changes significantly affecting the conduct of the study, and/or increasing risk to the subjects.

**2. Retention of Records**

Study records must be retained by the Investigator or Designee for a minimum of 2 years from the Investigator's study termination date, or per applicable regulatory and/or IRB or EC requirements (whichever time period is greater). Measures shall be taken to prevent accidental or premature destruction.

**D. Management of Incurrent Events**

**1. Failure to Obtain Informed Consent**

Study data will not be collected until the Informed Consent has been

signed and dated by the candidate. If a candidate does not wish to participate (does not sign and date the Informed Consent), data for that candidate will not be collected for this study.

2. Adverse Events

An adverse event is any unfavorable or unintended sign, symptom, or disease that impacts the subject. Adverse event is synonymous with complication or medical event.

See Section IX, Subsection E of this protocol for additional information regarding adverse event classifications. Femur related, serious, and unanticipated events are required to be reported on the **Adverse Event Report** case report form. The completed **Adverse Event Report** case report form must be submitted to the Sponsor in a timely manner. The Investigator or Designee will also promptly provide the Sponsor with any additional requested information required for the Sponsor to comply with regulatory requirements. If applicable per their reporting requirements, the Investigator or Designee will also report applicable adverse event(s) to their IRB or EC.

3. Revision

In the event that removal of one or more of the study related components is necessary (due to complication), the Investigator will determine the best treatment and/or revision method for the subject. Once the revision surgery has been completed, the Investigator or qualified Designee must complete an **Adverse Event Report** case report form as well as a **Study Completion** case report form terminating the subject from the study.

4. Investigator Withdrawal

The Investigator can choose to withdraw a subject from the study if the subject no longer meets study inclusion/exclusion criteria. The reason for the Investigator's withdrawal of the subject must be documented on the **Study Completion** case report form.

5. Subject Withdrawal

Study subjects may choose to withdraw from the study at any time, for any reason. If possible, a final evaluation will be completed for any subject who no longer wishes to participate in the study. The reason for the subject withdrawal must be documented on the **Study Completion** case report form.

6. Lost to Follow-up

A study subject will be considered lost to follow-up after they have missed a visit and a reasonable number of attempts to locate and evaluate them have failed. All attempts to contact the subject are to be documented in the subject's medical record and on the **Study Completion** case report form. In particular, the reason for the Study Completion must be documented. Missed visit(s) also must be documented using the **Protocol Deviation** case report form, unless the visit is retrospective.

7. Protocol Deviations

Investigators should not deviate from the study protocol. If a protocol deviation does occur, the deviation must be documented on the **Protocol Deviation** case report form and submitted to the Sponsor. If applicable per their reporting requirements, the Investigator or Designee will also report applicable protocol deviations to their IRB or EC.

8. Study Termination

Study subject participation is expected to end upon completion of the subject's 1 year follow-up visit unless the subject voluntarily withdraws from the study, is withdrawn from the study by the Investigator, is lost to follow-up, undergoes revision to remove a study device, (due to complication) including partial removal i.e. screw, or expires. Reason(s) for study completion must be documented on the **Study Completion** case report form.

If the Sponsor decides to terminate the study early, the Sponsor will inform the Investigators of the reason for early study termination. It is the responsibility of the Investigators to inform their IRB or EC as applicable according to local and national laws/regulations.

9. Modification of the Protocol

All amendments to this clinical protocol shall be agreed to by the Sponsor and be recorded with a justification for the amendment prior to implementation. Approval of the applicable IRB or EC must be obtained prior to implementation, if required according to the local and/or national laws/regulations.

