## **VI. Study Population**

The study population for primary statistical analysis will be comprised of males and females who satisfy the inclusion/exclusion criteria outlined in this section of the protocol. In order to avoid potential selection bias, each Investigator will offer study participation to each consecutive eligible patient presenting as a candidate. Eligible candidates who express interest in study participation will be offered Informed Consent. Inclusion/Exclusion Criteria should not be evaluated until the study-specific consent form has been completed.

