### **A. Inclusion Criteria**

- a. Patient must be 18 years of age or older.
- b. Patient must be eligible for an open reduction and internal fixation of the proximal femur.
- c. Patient must have an intracapsular or intertrochanteric fracture.
- d. Patient must have need for alignment, stabilization, and reduction of bone fractures.
- e. Patient must have ability and willingness to follow postoperative care instructions until healing is complete.
- f. Patient must be in good nutritional state.
- g. Patient must be able and willing to sign the IRB/EC approved informed consent.

*Note: Patients who have previously received THP Hip Fracture Plating System may be enrolled in the study if informed consent occurs prior to the end of the 6 weeks follow-up visit window.*

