## B. Exclusion Criteria

- a. Patient is a prisoner.
- b. Patient is a current alcohol or drug abuser.
- c. Patient is known to be pregnant or breastfeeding.
- d. Patient has a psychiatric illness or cognitive deficit that will not allow proper informed consent.
- e. Infection.
- f. Patient conditions including bloody supply limitations, obesity or insufficient quantity or quality of bone.
- g. Patient with mental or neurologic conditions who are unwilling or incapable of following postoperative care instructions.
- h. Patient has foreign body sensitivity. Where material sensitivity is suspected or unknown, testing is to be completed prior to implantation of the device.
- i. Patient is expected to be non-compliant with recommended post-operative weight-bearing instructions.

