### **D. Subject Enrollment**

Once the Informed Consent has been signed and dated by the subject, the subject will be considered enrolled in the study. A unique case identification number (Case ID) will be assigned to each participating subject/femur (bilateral subjects will be assigned a unique case ID number for each femur). This unique case ID number will be used throughout the study for identification. Case ID numbers will be assigned consecutively in ascending order per site, with the starting number for a given site defined by the Sponsor.

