### 3. Outcome Definitions

The outcome is in relationship to the Adverse Event, not the treatment rendered for the event (if any).

*Resolved:*

The adverse event has been resolved and/or no further treatment is required to treat the reported condition or illness.

*Tolerated:*

The adverse event will most likely never be resolved. The subject "tolerates" the illness or condition as a matter of life.

*Pending:*

Treatment or diagnostic studies were prescribed for the adverse event and the outcome of the adverse event is not yet known.

*Study Withdrawal:*

Due to the adverse event, the subject was withdrawn from the study.

*Device Removal:*

The adverse event resulted in the removal of a study device.

*Reoperation of Affected Joint:*

The adverse event resulted in reoperation of the study joint, but the reoperation did not include removal of a study device.

*Death:*

The outcome indicates the subject died as a direct result of the

reported adverse event.

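### Investigator withdrawal for lost eligibility (IX.D.4) is not confined to the time before implantation, so later revisions can go unrecorded and the 12-month revision rate could read slightly low (minor)

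*Combined protocol and SAP*

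**What the plan says.** All references are to the combined protocol and SAP.

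- **Withdrawal rule.** IX.D.4: "The Investigator can choose to withdraw a subject from the study if the subject no longer meets study inclusion/exclusion criteria". The reason goes on the Study Completion form. No time limit is given. The final evaluation where possible, in IX.D.5, covers only subjects who withdraw themselves.
- **Effect of withdrawal.** VIII.I collects data until, among other exits, the subject "is withdrawn from the study by the investigator, is lost to follow-up, undergoes revision to remove a study device". IX.D.8 expects participation to run to the 1-year visit "unless the subject voluntarily withdraws from the study, is withdrawn from the study by the Investigator".
- **Timing of eligibility.** VIII.D: "Once the Informed Consent has been signed and dated by the subject, the subject will be considered enrolled in the study". Section VI has the criteria evaluated only after consent, and Section V allows consent after surgery, up to the end of the 6-week visit window.
- **Criteria that could be read as lapsing after surgery.** VI.A: "Patient must have ability and willingness to follow postoperative care instructions until healing is complete". VI.B: "Patient is expected to be non-compliant with recommended post-operative weight-bearing instructions". VI.B also lists infection.
- **Analysis population.** Section VI: "The study population for primary statistical analysis will be comprised of males and females who satisfy the inclusion/exclusion criteria". It does not say at what date this is judged.
- **Endpoint and method.** Section IV defines the primary endpoint as a 12-month revision rate and assigns Kaplan-Meier to implant survival, counting intended as well as actual removal. XI.A gives counts and percentages for categorical data and Kaplan-Meier for implant survival, with no denominator or censoring rule.
- **Benchmark.** XI.B gives historical revision rates of about 20% (intracapsular) and 7% (intertrochanteric), assumed device rates of 15% and 5%, a margin of 8%, maxima of 101 and 89 subjects, and 15% loss to follow-up.
- **Revised subjects.** VIII.I and IX.D.3 end participation at revision for a complication. The Section II table lists X-rays and, as applicable, the radiographic assessment with RUSH at revision.

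**The concern.** One ordinary use of IX.D.4 is harmless: a subject consents, is then found ineligible before surgery, and is removed. The rule as written reaches further. A subject with the implant in place who stops following care instructions, or develops an infection, could be said to have stopped meeting the criteria. Such grounds may be related to revision risk, although the documents do not quantify this. The treating investigator makes the decision.

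After withdrawal, nothing in the plan brings a later revision into the data. There is no concurrent control arm in which the same loss could cancel, and the result is set against fixed historical rates, so missed revisions would favour the device.

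The secondary point concerns a different endpoint. Revision ends follow-up and XI.A summarises the data collected, so 6- and 12-month healing summaries omit subjects revised earlier. Healing among those still followed can then look better than healing among all implanted subjects.

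**Working it through.** **1. The plan's own figure.** The point does not rest on a sample-size error. Reading the 8% margin as percentage points, the bounds are 20% + 8% = 28% and 7% + 8% = 15%. With n = [z(1−α)√(p0·q0) + z(power)√(p1·q1)]² / (p0 − p1)², where q = 1 − p, and assuming one-sided α = 0.05 and 90% power (neither is stated):
- Intracapsular: (1.645 × 0.449 + 1.282 × 0.357)² / 0.13² gives 85; 85/0.85 = 100 (plan: 101).
- Intertrochanteric: (1.645 × 0.357 + 1.282 × 0.218)² / 0.10² gives 76; 76/0.85 gives 90 (plan: 89).

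**2. Evaluable numbers.** 0.85 × 101 = 85.9, so 86. 0.85 × 89 = 75.7, so 76.

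**3. Bias if withdrawn subjects are censored or excluded.** Let R be the true rate, w the share withdrawn before any revision is seen, and k their risk relative to stayers. The observed rate is the stayers' rate, R0 = R/(wk + 1 − w). Both w and k are assumptions.

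| w, k | 20% reads | 7% reads |
|---|---|---|
| 2%, 2 | 20/1.02 = 19.6% | 7/1.02 = 6.9% |
| 5%, 2 | 20/1.05 = 19.0% | 7/1.05 = 6.7% |
| 5%, 1 | 20% | 7% |
| 5%, 0.5 | 20/0.975 = 20.5% | 7/0.975 = 7.2% |

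If a fraction f of the revision risk has passed at withdrawal, the Kaplan-Meier rate is 1 − (1 − fR)(1 − R0)/(1 − fR0). With w = 5%, k = 2 and f = 0.5, this gives 19.5% and 6.8%.

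**4. Bias if withdrawn subjects are kept as unrevised.** At average risk (k = 1) the crude rate is R(1 − w): 0.95 × 20% = 19.0% and 0.95 × 7% = 6.65%. No excess risk is needed.

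**5. Effect on a non-inferiority reading.** The plan gives a margin but no test. Assume success means that the exact (Clopper-Pearson) two-sided 95% upper limit lies below the bound. The largest passing counts are 15/86 (upper limit 27.1%) and 5/76 (14.7%). The chance of passing with the true rate on the bound is P(X ≤ 15 | 86, b) or P(X ≤ 5 | 76, b), where b is the biased rate:

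| Case (censored) | Intracapsular | Intertrochanteric |
|---|---|---|
| No bias (b = 28%, 15%) | 1.6% | 2.1% |
| w 2%, k 2, early (27.5%, 14.7%) | 2.1% | 2.5% |
| w 5%, k 2, early (26.7%, 14.3%) | 3.1% | 3.1% |
| w 5%, k 2, f = 0.5 (27.2%, 14.6%) | 2.4% | 2.6% |

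These hold n fixed, with withdrawals inside the planned 15% loss. If 5% early withdrawals come on top of that loss, the cut-off must be recomputed at each reduced n, for the no-bias case as well. Error then rises from 1.8% to 3.3% and from 1.3% to 1.9%. With a one-sided 95% limit (16/86 and 6/76, n fixed), the 5% early case moves error from 3.1% to 5.5% and from 5.0% to 6.9%.

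**6. Secondary point.** At the assumed revision rates, 0.15 × 86 = 12.9 and 0.05 × 76 = 3.8, so about 13 and 4 subjects are absent from 12-month healing summaries. If none had healed before revision, counting them as not healed multiplies the unrevised-only healed share by 1 − 0.15 = 0.85 and 1 − 0.05 = 0.95. Earlier healing in some of them narrows the gap.

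**The case against.** - **The criteria describe baseline.** Expected non-compliance is a forecast and infection is naturally a condition at screening. The lists in VIII.I and IX.D.8 are general lists of exits. This is a fair reading of intent, but the text does not impose it, and VIII.I places investigator withdrawal among the events that end post-operative collection. IX.E.3 also has an adverse-event outcome, "Due to the adverse event, the subject was withdrawn from the study", though it does not say who withdraws the subject.
- **The effect is small.** This stands. At 2% withdrawn the rates barely move, and only the 5% early case takes the assumed two-sided rule clearly above 2.5%. Withdrawn share, relative risk, timing and test are all assumed, and Section XI makes the reports descriptive.
- **Other exits have the same gap.** Loss to follow-up (15% expected) and subject withdrawal also end data collection with no missing-outcome rule, and together may matter more. This stands. Investigator withdrawal differs in being at the study's discretion and easy to limit.
- **The withdrawals are visible.** Reasons are recorded and can be tabulated. Later revision status still cannot be recovered. Counting intended removal in implant survival narrows the gap without closing it.
- **Healing failures are not hidden.** Qualifying revisions are the primary endpoint, and X-rays and, as applicable, RUSH are listed at revision. This stands, and keeps the healing point secondary.

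**Conclusion.** The point holds as a minor one. IX.D.4 permits an implanted subject to be withdrawn on post-operative grounds, and any later revision then has no stated route into the primary endpoint. The rate could be too low: under censoring or exclusion, only if those withdrawn have above-average risk; under a crude rate that keeps them as unrevised, at any non-zero risk. In the illustration the shift is at most about one percentage point for intracapsular and a third of a point for intertrochanteric fractures. It rests on an assumed 5% withdrawn share, because the documents give none.

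Stronger readings are not supported:
- A reader might infer that the revision rate **is** biased. Withdrawal is optional, its frequency is unknown, and under censoring equal risk gives no bias and lower risk reverses it.
- A reader might infer that revisions in general go missing. Those before withdrawal are captured on the Adverse Event and Study Completion forms.
- A reader might infer that ending follow-up at revision distorts the primary endpoint. It does not affect time to first qualifying revision; it affects only healing and function summaries.

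**What to change.** **IX.D.4.** Limit investigator withdrawal for eligibility to the time before implantation. For post-operative enrolment, limit it to the eligibility check at enrolment, using pre-operative and operative records. After that, record a lapse as a protocol deviation or adverse event, keep the subject in the primary analysis, and follow revision status to 12 months where consent allows.

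**VI.** State that eligibility for the primary analysis is judged at that check and not later.

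**Reporting.** Give the number of, and reasons for, investigator withdrawals by fracture group; the reasons are already collected.

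**XI.A (secondary point).** Report healing with subjects revised for a device-related complication or non-union before documented healing counted as not healed. Give the unrevised-only summary as supportive.

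**Cost.** A few sentences in IX.D.4, VI and XI.A, with no new visits or procedures. A few more subjects stay in follow-up, and the healing figures may be slightly less favourable.

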### **B. Sample Size**

Due to the different historical revision rates for intertrochanteric fractures (~7%) and intracapsular fractures (~20%), study enrollment will be split between the two groups to maintain the integrity of the sample size with an expectant lost to follow-up rate of 15%. Intertrochanteric fractures will be limited to a maximum of 89 enrolled subjects and intracapsular fractures will be limited to a maximum of 101 enrolled subjects. This will provide enough evaluable data for both indications to show the necessary statistical improvement from the historical revision rates. The assumed revision rate of the THP Hip Fracture Plating System is 15% for intracapsular fractures and 5% for intertrochanteric fractures with a non-inferiority margin of 8%.

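### The lost-to-follow-up rule can close a subject out after one missed visit, with no provision for re-entry, renewed contact or a records check before the 12-month revision endpoint

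*Combined protocol and SAP*

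**What the plan says.** Section IX.D.6 sets the trigger: a subject is "considered lost to follow-up after they have missed a visit and a reasonable number of attempts to locate and evaluate them have failed". One missed visit is enough if contact then fails. The section gives no minimum number of attempts, no waiting period and no time at which the declaration is made. The attempts are recorded on the Study Completion form, and "In particular, the reason for the Study Completion must be documented". A missed visit is also logged as a protocol deviation, so a miss alone does not end participation.

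Section VIII.I sets the consequence. It says that "data will continue to be collected until the subject completes the study per the protocol, voluntarily withdraws from the study", and the list of ending events goes on to a subject who "is withdrawn from the study by the investigator, is lost to follow-up, undergoes revision to remove a study device". Section IX.D.8 does the same for participation: "Study subject participation is expected to end upon completion of the subject's 1 year follow-up visit unless the subject voluntarily withdraws", with loss to follow-up again among the exceptions.

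Four other places bear on the point:
- Section IV defines the primary endpoint as the revision rate at 12 months, for device-related complication or non-union.
- Section VIII.J says that "the expectation is to maintain the highest possible rate of follow-up compliance throughout this study".
- Section XI.A summarises implant survival by Kaplan-Meier. It gives no censoring rule and no sensitivity analysis for missing outcomes.
- Section XI.B plans for 15% loss, with caps of 101 intracapsular and 89 intertrochanteric subjects.

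**The concern.** The rule can turn a temporary absence into a permanent gap in the primary endpoint. A subject who cannot be reached around the 3-month visit may be closed out, and nothing then tells the site to try again at 6 or 12 months, to take the subject back if they reappear, or to look in its own records. A revision is a surgical event that the treating hospital's chart can show without a study visit. Chart review is already accepted in this study: Sections V and VIII.G use it for pre-operative and operative data on subjects who consent late. Loss is also listed separately from voluntary withdrawal, so a lost subject has not refused further data collection.

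In hip fracture patients a missed visit may itself reflect a complication, a readmission elsewhere, institutional care or death. If so, censoring at loss is informative and Kaplan-Meier understates the revision rate. Serious adverse events after close-out may be missed in the same way.

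**Working it through.** **1. Unobserved time.** Inputs are the windows in Sections II and VIII.I and the 12-month endpoint in Section IV, counting 3 months as 91 days and 12 months as 365.
- 3-month window: 91 ± 30 = day 61 to 121.
- Endpoint time remaining after day 121: 365 − 121 = 244 days, about 8 months.

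**2. The plan's own sample size.** Section XI.B gives historical rates of about 20% and 7%, assumed device rates of 15% and 5%, a margin of 8 points and 15% loss, but no alpha or power. I assumed a one-sample test against p_n = historical rate + 8 points, with one-sided alpha 0.05 and 90% power:

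n = [z(0.95)·√(p_n(1−p_n)) + z(0.90)·√(p_1(1−p_1))]² / (p_n − p_1)²

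- Intracapsular, 0.28 against 0.15: n = 84.66, rounded up to 85; 85/0.85 = 100 (plan: 101).
- Intertrochanteric, 0.15 against 0.05: n = 75.11, rounded up to 76; 76/0.85 = 89.4, rounded up to 90 (plan: 89).

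Under these assumptions the caps reproduce to within one subject per group, with the 15% entering only as inflation.

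**3. Subjects concerned.**
- Intracapsular: 0.15 × 101 = 15.2, about 15 lost and 86 evaluable.
- Intertrochanteric: 0.15 × 89 = 13.4, about 13 lost and 76 evaluable.
- Together about 28.

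**4. Upper illustration of bias.** Let p be the rate in retained subjects (the planned rate) and k the risk ratio of lost to retained subjects. The values of k are assumed; the documents give none. Suppose all of the lost subjects' risk falls after loss. The true rate is 0.85p + 0.15kp, Kaplan-Meier estimates p, and the understatement is 0.15p(k − 1).

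| Group | k = 1 | k = 2 | k = 3 |
|---|---|---|---|
| Intracapsular, p = 15%: true rate | 15.0% | 17.25% | 19.5% |
| Understatement (points) | 0 | 2.25 | 4.5 |
| Intertrochanteric, p = 5%: true rate | 5.0% | 5.75% | 6.5% |
| Understatement (points) | 0 | 0.75 | 1.5 |

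**5. The same in events.** With k from 1 to 3 and 25% to 100% of the risk falling after loss, unobserved revisions number:
- Intracapsular: from 15 × 0.15 × 0.25 = 0.6 to 15 × 0.45 = 6.8, against 86 × 0.15 = 12.9 expected in evaluable subjects.
- Intertrochanteric: from 13 × 0.05 × 0.25 = 0.2 to 13 × 0.15 = 2.0, against 76 × 0.05 = 3.8 expected.

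At k = 1 the missed events cost precision but do not bias the Kaplan-Meier estimate.

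**The case against.** The strongest reply is that the text is looser than it looks. Failed attempts are required as well as a missed visit, and no deadline is set, so a site could keep trying into later windows. A reader might infer that every such subject is closed out at month 4. The documents permit that but do not require it. The looseness does leave up to 10 sites free to apply the rule differently.

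A reader might also infer that a later revision or serious event has no route into the study. That is too strong. No sentence bars re-entry. Sections IX.D.2 and IX.D.3 call for adverse event reports without stating that the subject must still be active, and Section II requires a Product Experience Report for device-related events. What stands is that nothing places such an event in the study dataset for a closed subject, while Section VIII.I says collection has ended.

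Counting to the end of the 12-month visit window (day 455) would give 455 − 121 = 334 days, about 11 months. The endpoint is revision at 12 months, so 244 days is the relevant gap.

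It would also be wrong to read the table as the bias caused by this rule. Many of the 15% would be lost under any definition, the risk ratio has no source in the documents, and some risk may fall before loss. Nor should the understatement be set directly against the 8-point margin. If the limits are historical rate plus 8 (28% and 15%), the planned rates leave 13 and 10 points, and even 19.5% and 6.5% lie below the historical 20% and 7%. No figure in the documents sizes any bias in serious adverse event rates.

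Finally, Section VIII.J contains figures that are not shown, and the Appendix B forms are not available here. The statement that no records check is planned therefore covers the readable text only. Section VIII.J states an expectation that the rule fails to support; the two do not contradict each other.

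**Conclusion.** The point holds as a gap in ascertainment; it is not an arithmetic error. As written, Sections IX.D.6, VIII.I and IX.D.8 allow obtainable primary-endpoint and safety data to be discarded. In the 3-month example, up to about 8 months of the 12-month endpoint go unobserved.

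The documents do not determine the size or even the presence of bias. It is zero if loss is unrelated to revision risk. Under the assumed 1 to 3 times risk, with 15% loss and all of that risk after loss, the understatement is at most 4.5 points (intracapsular) and 1.5 points (intertrochanteric). A better rule recovers only the part that comes from subjects who return or whose charts show the event. The change is worth making because it is cheap and protects the primary endpoint; the sample size does not change.

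**What to change.** Reword Section IX.D.6, with matching edits in Sections VIII.I and IX.D.8, so that:
- a missed visit is recorded as a protocol deviation and the subject stays in the study;
- contact is tried again at each later scheduled visit, and a subject who returns resumes the schedule;
- loss to follow-up is finalised only after the 12-month window (365 + 90 = day 455) has closed without contact;
- before filing the Study Completion form, the site checks its own records for revision, reoperation, readmission and death within 12 months of surgery and enters any found;
- a subject without a revision is censored at the last date on which their status is known.

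Voluntary withdrawal stays as it is. The cost is protocol wording, a few more contact attempts and about 28 chart checks at the planned loss rate. Some charts will show nothing after the last contact and add no information.
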